4.2. Current state of the art

Current hemodynamic post-CA guidelines state that “*Fluid administration as well as vasoactive (e.g. norepinephrine), inotropic (e.g. dobutamine) and inodilator (e.g. milrinone) agents should be titrated to optimize blood pressure, cardiac output and systemic perfusion (class I, level of evidence B). Although human studies have not established robust targets for blood pressure or blood oxygenation, a mean arterial pressure above 65mmHg is generally considered to be a reasonable goal*

(Peberdy et al, Circulation 2010).

It is important to emphasize that these recommendations are not based on mortality data in post-cardiac arrest patients. Nor has it been shown or even investigated that a blood pressure of 65mmHg would result in optimal brain perfusion in post-cardiac arrest patients. Instead, these guidelines are adapted from sepsis guidelines based on the unsubstantiated assumption that the post- cardiac arrest syndrome is a sepsis like syndrome. Moreover, the true value of goal direct therapy in sepsis has recently been questioned (*Peake et al, NEJM 2014*). All the above emphasize the need for objective and properly validated guidelines for hemodynamic support in the post-CA setting.

4.3. Observational studies on new hemodynamic targets

During intensive care unit stay after cardiac arrest, the optimal MAP and cardiac output should maintain optimal cerebral perfusion to avoid additional cerebral ischemic damage caused by cerebral hypo- and hyper perfusion.

In a first study, we showed that there is a large inaccuracy regarding cardiac output measurements by conventional continuous thermodilution in CA patients treated with therapeutic hypothermia. In contrast, cardiac output calculated by means of continuous SVO₂ using the Fick equation was shown to be a valuable alternative in patients treated with therapeutic hypothermia (*Ameloot et al, Resuscitation 2014*).

In a second observational trial, we constructed a hemodynamic model to determine the optimal MAP and SVO₂ range associated with optimal cerebral oxygen saturation (*Ameloot et al, resuscitation 2015*). It was previously shown that in a subset of post-CA patients (mainly these with chronic hypertension) the lower threshold of cerebral autoregulation is shifted rightward towards higher systemic blood pressures and these patients might benefit from resuscitation to higher MAP's to preserve adequate cerebral perfusion (*Sundgreen, Stroke 001*). In contrast, many post-CA patients have a reduced left ventricular function and might benefit from afterload reduction to maintain stroke volume and cerebral perfusion. Therefore, we hypothesized that the optimal MAP should maintain cerebral perfusion without exposing the damaged myocardium to excessive afterload. The relationship between MAP, SVO₂ and cerebral saturation is shown in the figure below (n=1 635 827 data points obtained in 41 patients during the first 24 hours after ICU admission). We found a strong linear relationship between MAP and cerebral saturation in the MAP range between 45 and 101mmHg (R^2

0.83). Mean arterial blood pressures above 101mmHg were associated with progressively decreasing cerebral saturations ($R^2 0.72$).

Additionally, MAP's above 101mmHg were also associated with progressively decreasing SVO₂'s suggesting that this excessive left ventricular afterload impairs cardiac output and by consequence cerebral perfusion. The currently recommended MAP of 65mmHg clearly resulted in a submaximal cerebral saturation. The lowest optimal MAP based on this hemodynamic model was determined to be 87mmHg since the cerebral saturation corresponding with this MAP of 87mmHg was 67.6% and almost equal to the average of all calculated cerebral saturations associated with higher MAP values (average 67.5%). Cerebral saturation is maximized at a MAP of 101mmHg. Therefore, the MAP range associated with optimal cerebral oxygenation was determined to be between 87-101mmHg. The corresponding SVO₂ range associated with optimal cerebral oxygenation was determined to be between 70-75%. Both the suggested MAP (87-101mmHg) and the SVO₂ range (70-75%) resulted in cerebral saturations between 67-69%.

[figure not shown]

Figure 1: Relationship between mean arterial pressure (MAP), mixed venous oxygen saturation (SVO₂) and cerebral saturation (SctO₂).

In a third observational trial, we focussed on cerebral autoregulation. We confirmed the previous findings by Sundgreen et al (*Stroke* 2001) that cerebral autoregulation is shifted rightward in 35% of post-cardiac arrest patients. Phenotypically, a higher proportion of patients with disturbed autoregulation had pre-cardiac arrest hypertension (65±49 vs 31±47%, $P=0.02$) suggesting that right shifting of autoregulation is caused by chronic adaptation of cerebral blood flow to pre-existing higher blood pressures. In multivariate analysis, patients with preserved autoregulation had a significantly higher 180-days survival rate (odds ratio 4.62). Finally, we defined the optimal MAP range within the autoregulatory zone as defined by an index of autoregulation (COX). COX was calculated as a *linear correlation coefficient between 10 seconds averaged values of brain saturation and MAP, that is continuously changing and recorded over 5 minute time windows during the 24 hours study period*. In this way, COX is a continuous variable that ranges from -1 to +1 and that can be used as a robust surrogate marker of autoregulation at a specific time point. Intact autoregulation is indicated by negative or near-zero COX because

small MAP variations will not alter cerebral oxygenation when autoregulation is active. When autoregulation becomes impaired, COX becomes positive because MAP and SctO₂ correlate indicative of MAP-dependency of cerebral saturation. We averaged all obtained COX values per 5mmHg MAP bins and generated bar graphs to identify the COX predicted optimal MAP range as the MAP bins with negative or near-zero COX values. When COX per 5 mmHg bar graphs were pooled and averaged over all 51 study patients, the overall COX predicted optimal MAP was between 85 and 105mmHg (see figure below).

[figure not shown]

Figure 2: Pooled COX per 5 mmHg MAP plot. The MAP range associated with optimal autoregulation (negative COX values) was defined to be between 85-105mmHg.

In summary, we found that the MAP range associated with optimal cerebral perfusion corresponds with the MAP range within the autoregulatory zone (85- 100/105mmHg).

Is there any evidence from observational studies that a higher MAP would be associated with a better neurological outcome? In our own observational study (*Ameloot et al, resuscitation 2015*), we showed that the MAP range associated with the highest odds ratio for survival was 76-86 mmHg (OR 2.63, 95% CI [1.01; 6.88], p=0.04). The SVO₂ range associated with the highest odds ratio for survival was 67-72% (OR 8.23, 95% CI [2.07; 32.68], p=0.001). Logistic regression revealed that the probability of survival increased with increasing percentage of time within the optimal MAP (OR 1.04 per % in the optimal range, 95% CI [1.00; 1.07], p=0.001) and SVO₂.

range (OR 1.03 per % in the optimal range, 95% CI [1.00; 1.05], p=0.04). An average MAP>65 mmHg or SVO₂>70% were not associated with increased survival highlighting marked limitations of current patient management recommendations. In two separate models using backward multiple logistic regression, a mean MAP in the optimal range (OR 3.72, 95% CI [1.11; 12.50], p=0.03) and a mean SVO₂ in the optimal range (OR 10.32, 95% CI [2.03; 52.60], p=0.001) remained independently associated with increased survival.

Our findings are in agreement with 2 retrospective and 1 prospective observational study on the positive association between higher MAP's during the first 6 hours post-ROSC and increased survival in post-cardiac arrest patients (*Beylin, ICM 2013*; *Trzeciak, Crit Care Med. 2009*; *Kilgannon, Crit Care Med. 2014*). In contrast with these observational trials, in the Neuroprotect post-CA trial the intervention strategy will be extended until 36 hours after admission. Is there any evidence from non-randomized controlled trials that forcing MAP or SVO₂ into the suggested range with additional pharmacological support would improve outcome? In a small study by *Gaieski et al*, 20 prospective post-cardiac arrest patients received early goal directed hemodynamic optimization with a target central venous saturation above 65% and MAP between 80-100mmHg. A trend toward better survival was observed in treated patients (50% survival) when compared with 18 historic controls (22% survival) (*Gaieski, Resuscitation 2009*). This study, however, is limited by the small sample size and extremely low survival rates in the historic control group.

We have shown that the currently recommended MAP target of 65mmHg results in a suboptimal cerebral saturation beyond the autoregulatory range. Moreover, analysis of available patient data thus far indicates that an average MAP above 65mmHg is not associated with a greater likelihood to survive with good neurological outcome compared with an average MAP below 65mmHg. In contrast, both our hemodynamic model and our preliminary study on cerebral autoregulation suggest that optimal cerebral perfusion is maintained with markedly higher MAP's (85-100mmHg) and normal SVO₂'s (70-75%). As shown above, 4 observational studies and one small prospective interventional with historic controls suggest that resuscitation to higher MAP's might confer better neurological outcome in post-cardiac arrest patients, which needs to be confirmed in adequately powered prospective randomized controlled studies. Here, we hypothesize that our proposed neuroprotective hemodynamic optimization strategy will reduce cerebral ischemia thereby improving

neurological outcome in post-cardiac arrest patients.

4.4. Innovative aspect of the Neuroprotect post-CA trial

The Neuroprotect post-CA trial will be the first randomized controlled trial to investigate whether forcing MAP and SVO₂ in the suggested range improves cerebral ischemia and neurological outcome in post-cardiac arrest patients. It has been shown that targeted temperature management to avoid the deleterious effects of fever, somewhat improves outcome of post-CA patients (*Nielsen, NEJM 2014*). Nevertheless, even with optimal targeted temperature management recovery with good functional outcome is limited to 40% of the post-CA patients. Apart from targeted temperature management, no single in hospital randomized controlled intervention trial has been able to improve outcome in these patients with a major unmet clinical need.

5. STUDY OBJECTIVES

The **primary objective** of the trial is to assess whether or not a new goal directed hemodynamic optimization strategy can reduce cerebral ischemia in post-CA patients as quantified by diffusion weighted MRI (DW-MRI) to be performed at day 4-5 with quantification of the percentage of ischemic voxels with an apparent diffusion coefficient (ADC) below 0.650 mm²/s.

Secondary efficacy outcomes:

- Cerebral performance category 3-5 at discharge from the ICU
CPC 1: return to normal cerebral function and normal living
CPC 2: Disability but sufficient function for independent activities of daily life
CPC 3: severe disability
CPC 4: Coma
CPC 5: Death
- Cerebral performance category 3-5 at 180 days post-CA (assessed by trial investigators that are unaware of the treatment assignment)
- Neurocognitive testing at discharge from the hospital
- Biomarkers: Neuron specific enolase (day 1-2-3-4-5)
- Functional testing: Activities Daily Life (ADL) and 6 minute walking distance (6MWD) at discharge from the hospital

- Renal function: creatinine day 1-2-3-4-5 and urinary output day 1-2-3-4-5
- Length of stay in the ICU
- Duration of mechanical ventilation
- Placement of tracheostomy

Safety outcomes:

- Incidence of life threatening arrhythmias during intervention period
- Incidence of new onset atrial fibrillation during intervention period
- Incidence of pulmonary congestion requiring diuretics during intervention period

6. INVESTIGATIONAL PLAN

6.1. Study Plan and Design

Multicenter randomized controlled open label trial conducted in 2 tertiary care hospitals in Belgium (UZ Leuven, and ZOL-Genk). Eligible patients will be randomly assigned in a 1:1 ratio to goal directed hemodynamic optimization or standard care strategy. Randomization will be performed centrally at the Leuven Coordinating Centre for Clinical Trials with the use of a computer-generated assignment sequence and an interactive voice response system. Patients will be stratified according to the presence of an initial shockable rhythm. Health care professionals caring for the trial patients will be aware of the intervention assignments because of the inherent problems with blinding of MAP. Physicians performing neurologic prognostication, radiologist interpreting MRI's, study personnel assessing final outcomes and statisticians will be unaware of the intervention assignments. Unblinding of all data and the final analysis of all primary and secondary outcome parameters will be performed after inclusion of all study patients. Written informed consent will be obtained from a next of kin. If a next of kin or another designated person is not available, a procedure for inclusion in the study in emergency situations will be applied. A definitive post hoc consent form will ultimately be obtained from patients who survived but had been initially treated on the basis of the emergency consent. The ethical committees in the participating hospitals will approve the study protocol prior to enrolment of the first patient.

6.2. Discussion of Study Design

A multicentre study is necessary to recruit an appropriate number of patients and guarantee generalizability of the study results.

6.3. Selection of Study Population

All patients presenting or referred to the investigational site after being successfully resuscitated from out of hospital CA will be screened for enrolment. All patients will be expected to meet all inclusion and exclusion criteria before entering the study. Minor deviations to these criteria may be allowed with prior approval of the principle investigator of the study site.

6.3.1. *Inclusion Criteria*

The patient must meet the following criteria:

1. Out-of-hospital CA of presumed cardiac cause irrespective of the presenting rhythm
2. Unconsciousness (Glasgow coma scale < 8) at hospital admission
3. Age \geq 18 years
4. Sustained return of spontaneous circulation (ROSC) (=when chest compressions have not been required for 20 consecutive minutes)

6.3.2. *Exclusion Criteria*

Exclusion Criteria:

1. Suspected or confirmed intracranial bleeding or stroke
2. Known limitations in therapy or Do Not Resuscitate-order
3. Known disease compromising 180 day survival
4. Known pre-CA cerebral performance category 3-4
5. Previous stroke (TIA can be included)
6. MRI incompatible cardiac or neurosurgical device
7. Systolic blood pressure < 90 mmHg on norepinephrine > 1 mcg/kg/min).
8. Open chest
9. ECMO (extracorporeal membrane oxygenation)
10. Pregnancy

6.3.3. *Withdrawal of Patients from Therapy or crossover*

In the intervention (“Neuroprotect post-CA”) group, a reduction in vasopressor doses to maintain a MAP of 65mmHg is recommended if any of the pre-specified serious adverse events that were potentially related to an increased rate of vasopressor infusion occurs. These events include: major ventricular arrhythmia requiring life support, electrical or pharmacological cardioversion, poorly tolerated supraventricular arrhythmia and peripheral limb ischemia.

Treatment may also be discontinued if the legal representative withdraws their consent.

All patients who are withdrawn from study treatment will have safety assessments completed during the entire course of the study.

6.3.4. Definition of Randomization and Completion

A patient will be considered 'randomized' when a randomization number has been assigned by the Interactive Voice Response System.

6.4. Baseline Characteristics to be collected

Baseline characteristics to be collected:

- Informed Consent
- Compliance with the inclusion/exclusion criteria will be documented
- Age
- Gender
- Medical history (chronic heart failure, previous AMI, previous cardiac surgery, previous arrhythmia, arterial hypertension, diabetes mellitus, COPD, chronic kidney disease, stroke)
- Chronic medication
- Arrest Characteristics (Public vs private place, bystander witnessed, bystander CPR performed, presenting rhythm, time to ROSC)
- Admission Characteristics (MAP, PaCO₂, PaO₂, Lactate, pupillary reflex, corneal reflex, FIO₂, dose of norepinephrine and dobutamine)
- Cause of arrest (STEMI, NSTEMI, arrhythmogenic, hypoxic, unknown)
- Angiography performed (time in hospital, time in cathlab, time in ICU)
- PCI performed
- SOFA score

6.5. Study treatments

6.5.1. Treatments Administered

In patients assigned to the intervention group, placement of an IABP will be considered in the catheterization laboratory if the dose of norepinephrine necessary to achieve a MAP of 65mmHg exceeds 0.5 mcg/kg/min. In patients assigned to the intervention group, a new generation pulmonary artery catheter (CCOmbo, Edwards life sciences) will be inserted. Other trial interventions will start immediately after ICU admission and a summary flow chart guiding the targeted interventions is presented in the figure below. In patients randomized to receive the intervention, the target mixed venous oxygen saturation (SVO₂) is between 65-75% and the target MAP is between 85-100mmHg. Arterial blood

gas analysis will be performed on an hourly basis by treating nurses and physicians during the first 36 hours after ICU admission. Calibration of the continuous SVO₂ monitor will be performed per 4 hours by a central venous blood gass. In the treatment protocol, we will include specific recommendations for uniform and homogeneous interventions across centres in response to changing hemodynamic variables.

	MAP < 85 mmHg	MAP 85-100 mmHg	MAP > 100 mmHg
SVO₂ < 65 %	
Step1: Fluid responsiveness?
 
 • Sinus: SVV > 12% • AF: Passive leg raising test 
7 Plasmalyte 500 cc/u (max 3l/24u)
 
Step2: Hemoglobin < 10 g/dl?
 
7 Transfusion 1 UPC
 
Step3: Heartrate < 40 SPM
 
7 Consider Isuprel of Pacing
 
Step4: Inotropics/vasopression
 
 • Dobutamine + 5 mcg/kg/min (max 20 mcg/kg/min) • Levophed + 0.05 mcg/kg/min per 10 minutes until MAP OK (max 1 mcg/kg/min) 	
Step1: Fluid responsiveness?
 
 • Sinus: SVV > 12% • AF: Passive leg raising test 
7 Plasmalyte 500 cc/u (max 3l/24u)
 
Step2: Hemoglobin < 10 g/dl?
 
7 Transfusion 1 UPC
 
Step3: Heartrate < 40 SPM
 
7 Consider Isuprel of Pacing
 
Step4: Inotropics/vasopression
 
 • Dobutamine + 5 mcg/kg/min (max 20 mcg/kg/min) 	
Step1: Fluid responsiveness?
 
 • Sinus: SVV > 12% • AF: Passive leg raising test 
7 Plasmalyte 500 cc/u (max 3l/24u)
 
Step2: Hemoglobin < 10 g/dl?
 
7 Transfusion 1 UPC
 
Step3: Heartrate < 40 SPM
 
7 Consider Isuprel of Pacing
 
Step4: Inotropics/vasopression
 
 • Dobutamine + 5 mcg/kg/min (max 20 mcg/kg/min)

SVO₂ 65-75%	Levophed + 0.05 mcg/kg/min per 10 minutes until MAP OK (max 1 mcg/kg/min)	OK (recheck after 1hour)	Levophed - 0.05 mcg/kg/min per 10 minutes until MAP OK
SVO₂ > 75%	Levophed + 0.05 mcg/kg/min per 10 minutes until MAP OK (max 1 mcg/kg/min)	
Step1: Inotropics
 
 • Dobutamine - 5 mcg/kg/min 
Step 2: Seloken 5mg/5 min IV if HR > 90 SBM
	
Step1: Inotropics/Vasopressors
 
 • Dobutamine - 5 mcg/kg/min • Levophed - 0.05 mcg/kg/min per 10 minutes until MAP OK 
Step 2: Seloken 5mg/5 min IV if HR > 90 SBM

Table 1: Hemodynamic interventions

In case of below target SVO₂, fluid status will be optimized if fluid responsiveness is anticipated as indicated by stroke volume variation (if sinus rhythm, full sedation, normal TV ventilation) or passive leg raising test (step 1), anemia will be corrected to maintain a hemoglobin above 10 g/dl (step 2), treatment of excessive bradycardia (heart rate <40 BPM) will be considered (step 3) and dobutamine will be infused (step 4) according to the study protocol. Additional fluid challenge will be limited to 3 liters/24 hours.

In case of below target MAP but normal SVO₂, norepinephrine will be infused.

In case SVO₂ exceeds 75%, dobutamine infusion rate will be reduced (step 1) and seloken 5mg IV (1mg/min) will be infused if heart rate exceeds 90 BPM and MAP 100mmHg in the absence of inotropic or vasopressive support (step 2).

In case MAP is greater than 100mmHg, norepinephrine infusion rate will be reduced (step 1) and seloken 5mg IV (1mg/min) will be infused if heart rate exceeds 100 BPM and SVO₂ 75% in the absence of inotropic or vasopressive support (step 2). In the intervention (“Neuroprotect post-CA”) group, a reduction in vasopressor doses to maintain a MAP of 65mmHg is recommended if any of the pre-specified serious adverse events that were potentially related to an increased rate of vasopressor infusion occurs. These events include: major ventricular arrhythmia requiring life support, electrical or pharmacological cardioversion, poorly tolerated supraventricular arrhythmia and peripheral limb ischemia.

In patients randomized to receive current standard of care, hemodynamic support will be at the discretion of the treating physician with a target MAP of 65mmHg. All the drugs used in the study will be purchased from manufacturers not involved in the study.

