### 3 Study Methods

#### 3.1 Overall Study Design and Plan

This was a prospective, multicentre, interventional, controlled, randomized, open-label investigator-driven study.

Patients were recruited at 2 tertiary care hospitals in Belgium (UZ Leuven and ZOL-Genk) and were randomized in a 1:1 ratio to either goal-directed hemodynamic optimization or standard care. In patients randomized to receive the intervention, the target mixed venous oxygen saturation (SVO2) was between 65-75% and the target mean arterial pressure (MAP) was between 85- 100mmHg. Fluid administration and hemodynamic support was adjusted according to a flow chart in case SVO2 or MAP were below or above the suggested targets on an hourly basis. The intervention lasted up to 36 hours after admission to ICU.

Once admitted to ICU, the patients were assessed hourly up to 36 hours after admission and daily up to 5 days after admission. Further assessments were done at discharge from ICU, discharge from the hospital and at 180 days after the initial cardiac arrest.

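### Protocol 6.5.1: Table 1 and the text give conflicting triggers for the IV beta-blocker (Seloken) in two of nine MAP/SVO2 cells, and neither document says which prevails

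*Protocol*

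**What the plan says.** Protocol 6.5.1 sets out the intervention in Table 1 (three SVO2 rows by three MAP columns) and again in the text that follows. Seloken appears in two table cells, SVO2 above 75% with MAP 85-100 and SVO2 above 75% with MAP above 100. In both, step 2 reads "Seloken 5mg/5 min IV if HR > 90 SBM". The table puts no condition on concurrent inotropes or vasopressors. Its step 1 lowers dobutamine in the first cell, and dobutamine and Levophed (norepinephrine) in the second.

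The text has two Seloken sentences. For SVO2 above 75%: "seloken 5mg IV (1mg/min) will be infused if heart rate exceeds 90 BPM and MAP 100mmHg in the absence of inotropic or vasopressive support". For MAP above 100 mmHg, Seloken "will be infused if heart rate exceeds 100 BPM", again with SVO2 at 75% as a condition and again only with no support running.

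On the standing of the two sources, 6.5.1 calls the table "a summary flow chart guiding the targeted interventions". SAP 3.1 reports that "Fluid administration and hemodynamic support was adjusted according to a flow chart", and the protocol synopsis says much the same in the future tense. The stated purpose in 6.5.1 is to give "specific recommendations for uniform and homogeneous interventions across centres".

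**The concern.** Section 6.5.1 defines what patients in the intervention arm receive. If its table and its text trigger a drug under different conditions, two sites can each follow the protocol and treat the same state differently. Here the drug is an intravenous beta-blocker in patients just resuscitated from cardiac arrest, and one point of difference is whether it may be given while inotropes or vasopressors are running. That is a patient-safety matter. It also works against the uniformity across centres that the section promises, and it leaves adherence to this step without a single standard. The documents do not show how often these states arose or whether the two sites differed in practice.

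**Working it through.** The plan gives no figure to reproduce. The check sets the three statements side by side as rules.

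**Rules (all from Protocol 6.5.1)**
- Table: SVO2 > 75%, MAP 85 or above, heart rate > 90.
- Text A (the SVO2 sentence): SVO2 > 75%, MAP > 100, heart rate > 90, no support running.
- Text B (the MAP sentence): MAP > 100, SVO2 > 75%, heart rate > 100, no support running.

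Text A gives MAP 100 mmHg without its own comparator. I read the preceding verb as covering it, so MAP above 100. Text B is built the same way for SVO2. Dose and rate do not conflict: 5 mg over 5 min is 5/5 = 1 mg/min in both sources.

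**Which cells are affected.** In the seven cells other than the two named above, no rule triggers Seloken. The two remaining cells, split by heart rate and support, give 2 × 3 × 2 = 12 states:

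| MAP (SVO2 > 75%) | Heart rate | Support | Table | Text A | Text B | All agree? |
|---|---|---|---|---|---|---|
| 85-100 | ≤90 | no | no | no | no | yes |
| 85-100 | ≤90 | yes | no | no | no | yes |
| 85-100 | 91-100 | no | give | no | no | **no** |
| 85-100 | 91-100 | yes | give | no | no | **no** |
| 85-100 | >100 | no | give | no | no | **no** |
| 85-100 | >100 | yes | give | no | no | **no** |
| >100 | ≤90 | no | no | no | no | yes |
| >100 | ≤90 | yes | no | no | no | yes |
| >100 | 91-100 | no | give | give | no | **no** |
| >100 | 91-100 | yes | give | no | no | **no** |
| >100 | >100 | no | give | give | give | yes |
| >100 | >100 | yes | give | no | no | **no** |

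**Counts**
- As written: 4 of 6 in the MAP 85-100 cell plus 3 of 6 in the MAP > 100 cell = 7 of 12.
- With the no-support condition read into the table, only the no-support rows count: 2 of 3 plus 1 of 3 = 3 of 6.
- If, in addition, either text sentence is enough on its own, Text B adds nothing, because every state that meets B also meets A. The MAP > 100 disagreement then disappears and 2 of 6 remain, both at MAP 85-100.

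**Examples without support.** At SVO2 78%, MAP 90, heart rate 95, the table leads to Seloken and neither text sentence does. At SVO2 78%, MAP 105, heart rate 95, the table and Text A call for it and Text B does not.

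**Two neighbouring cells, not counted**
- SVO2 > 75% with MAP < 85: the table lists only a Levophed increase. The text lists a dobutamine reduction, and its norepinephrine rule opens "In case of below target MAP but normal" SVO2, so it does not reach this cell. Both actions could be carried out together, but the sources have none in common. This is a gap.
- SVO2 < 65% with MAP > 100: the text lowers norepinephrine and the table cell, as it reads in the text copy, does not. A bullet may have been lost in conversion from PDF.

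**The case against.** Six points can be made on the other side.

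1. **The rules say when Seloken is given, not that it is otherwise forbidden.** A silent sentence need not contradict one that speaks. This has some force on the heart-rate difference at MAP above 100. It does not help at MAP 85-100: if Text A is only one sufficient condition beside the table, its MAP and no-support conditions restrict nothing.
2. **The table is a summary, and its step 1 reduces support first, so the text merely supplies detail.** This would remove the four disagreeing states with support running and leave 3 of 6. But step 1 at MAP 85-100 lowers dobutamine by 5 mcg/kg/min, while the table elsewhere allows up to 20, and it leaves Levophed untouched. Completing step 1 therefore does not mean that support is off.
3. **At MAP above 100 the heart-rate conflict is one text sentence against the other.** This is correct. The table agrees with Text A on heart rate there and differs from it only on support.
4. **The MAP condition rests on a reading.** That is also correct. The reading is the natural one, but the clause should be checked in the original.
5. **The synopsis and SAP 3.1 point to the flow chart as the working tool.** They do, but neither says what applies when chart and text differ. Section 6.5.1 also mentions recommendations to be included in the treatment protocol. If that is a separate document, it is not among those reviewed.
6. **Inclusion is complete, so an amendment protects no enrolled patient.** This stands. It limits what the fix can achieve but does not make the rule consistent.

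**Conclusion.** The concern holds. Table 1 and the text of 6.5.1 give different Seloken triggers in 2 of 9 cells, and the text also contradicts itself on heart rate (90 against 100) for SVO2 above 75% with MAP above 100. The size is 7 of 12 rule states as written, 3 of 6 if the table is taken to imply that no support is running, and 2 of 6 on the most lenient reading. In the MAP 85-100 cell the disagreement survives every one of these readings.

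The conclusion assumes that the text means MAP above 100 and that each stated condition is meant to restrict use. The state counts depend on the heart-rate bands chosen and say nothing about numbers of patients or hours. The absence of a precedence rule is established only for the protocol and the SAP. Sample size, alpha and the primary analysis are not affected. With inclusion complete, what is at stake is mainly an accurate account of the intervention as delivered, and the safety of any reuse of this protocol.

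**What to change.** Reconcile Table 1 with the text so that each cell has one heart-rate trigger, one MAP condition, one rule on concurrent support and one set of vasoactive actions, and state which source prevails if they differ. The choice of rule belongs to the clinical leads; this review takes no position on it. In the same edit, clarify the SVO2 > 75% / MAP < 85 cell, and check against the original PDF both the SVO2 < 65% / MAP > 100 cell and the MAP clause in the SVO2 sentence.

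For patients already treated, document which version each site used and do not judge them against the reconciled table. Section 6.6.2 lists hourly doses of norepinephrine, dobutamine and Isuprel but not Seloken, so its use would have to come from the usage log required by 6.5.4. The protocol does not say that the log records times. Without times it can show that Seloken was given but not which trigger was applied. With times, entries could be matched to the continuous heart rate, MAP and SVO2 recordings in 6.6.1.

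The cost is a wording amendment to one table and one paragraph, one documented query to each of the two sites, and a log look-up. No new procedure is needed, and the analysis sets do not change.
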